5.1.4.6 Treatment-Emergent Malignancies (Second Primary Malignancies)

Events of second primary malignancies have been reported across the venetoclax hematologic oncology program. However, no causal association with the venetoclax administration has been confirmed, and no pattern has been observed. The overall observed incidence rate of malignancy in the venetoclax clinical trial programs were comparable to that reported in the general population. The second primary malignancies will be closely monitored in this study.

5.1.5 Dose Modification

Reasons for dose modifications including dose delays, the supportive measures taken, and the outcomes will be documented in the patient's chart and recorded on the eCRF. The severity of adverse events will be graded according to NCI CTCAE v5.0.0.

- When several toxicities with different grades of severity occur at the same time, the dose modifications should be according to the highest grade observed.
- If, in the opinion of the investigator, a toxicity is considered to be due solely to one component of the study treatment and the dose or administration of that component is delayed or modified, the dose or administration of the other study treatment components do not require modification and may be administered if there is no contraindication.
- When treatment is temporarily interrupted because of toxicity caused by atezolizumab, carboplatin, or etoposide, the treatment cycles should be restarted such that the atezolizumab infusions remain synchronized and aligned with the chemotherapy schedule.
- If, in the opinion of the investigator, a toxicity is considered to be due solely to one chemotherapy drug, the dose of the other chemotherapy drug does not require modification.

The investigator may use discretion in modifying or accelerating the dose modification guidelines described below depending on the severity of toxicity and an assessment of the risk versus benefit for the patient, with the goal of maximizing patient compliance and access to supportive care.

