5.1.4.3 Serious Infections

Serious infection is an important identified risk for venetoclax. Infections have been reported in the oncology clinical studies; however, these events are confounded by the underlying disease, comorbidities, and other immunosuppressive medications. To date, no clear relationship has been noted between serious infectious events and neutropenia. The types of infectious events observed generally have been consistent with those anticipated in the elderly population of heavily pretreated subjects with hematologic malignancies and are similar across all indications. Infections are closely monitored in venetoclax program across all indications. Patients should be advised to report fever and should be assessed for further management as per standard medical practice. In the oncology studies, recommendations are included in the protocol regarding the need for anti-infective prophylaxis per standard of care (e.g., NCCN for oncology subjects).

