Diarrhea should be controlled with adequate anti-diarrheal medication. Nausea and/or vomiting may be controlled with adequate anti-emetics. For Grade 3 or 4 neurotoxicity, chemotherapy should be resumed at 50% of the previous dose upon improvement or discontinued immediately (based on investigator's clinical judgment).

Suggested recommendations for dose modification of etoposide for renal impairment are provided in Table 9.

Table 9 Etoposide Dose Modification for Renal Impairment

Creatinine Clearance (mL/min)	Etoposide Dose	
> 50	100%	
15–50	75% of dose	

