Neutropenia, Grade 3 (ANC < 1000–500/mm³) ^a	 Withhold venetoclax. If counts recover to ANC 1500/mm³: Resume treatment with venetoclax at previous dose. Administer atezolizumab plus carboplatin and etoposide at previous dose during induction treatment. .
Neutropenia, Grade 4 (ANC count < 500/mm ³) ^a	 Withhold venetoclax. Withhold atezolizumab plus carboplatin and etoposide. Administer treatment including G-CSF or growth factors for neutropenia as indicated or as per institutional guidelines. If counts recover to ANC 1500/mm³: Resume venetoclax at one dose level reduction (see Table 6). Administer carboplatin and etoposide at 75% of previous dose (see Table 7). Dose of carboplatin and etoposide can be re-escalated (even to full dose) in subsequent cycles with the approval of Medical Monitor (see Section 5.1.5.2). Administer atezolizumab at previous dose level. If patient develops recurrent Grade 4 neutropenia despite growth factor support and following venetoclax dose reduction to 100 mg and two dose reductions for carboplatin etoposide, discontinue venetoclay and carboplatin etoposide during the induction phase
Febrile neutropenia, Grade 3-4 (ANC < 1000/μL) plus fever of > 38.5°C	 Withhold venetoclax. Withhold atezolizumab plus carboplatin and etoposide. Administer treatment with growth factors per institutional guidelines. Upon resolution of Grade ≥ 3 febrile neutropenia (ANC > 1500/mm³): Resume venetoclax at one dose level reduction (see Table 6). Administer carboplatin and etoposide at 75% of previous dose (see Table 7). Dose of carboplatin and etoposide can be re-escalated (even to full dose) in subsequent cycles with the approval of Medical Monitor (see Section 5.1.5.2). Administer atezolizumab at previous dose level. If patient develops recurrent Grade -34 febrile neutropenia despite growth factor support and following venetoclax dose reduction to 100 mg and two dose reductions for carboplatin etoposide, discontinue venetoclax and carboplatin etoposide during the induction phase.

Table 10Management Guidelines for Specific Adverse Events with
Venetoclax, Atezolizumab, and Carboplatin Etoposide (cont.)

Event	Management		
Thrombocytopenia, Grade 3 (platelet count	 Withhold venetoclax. Withhold atezolizumab plus carbonlatin etoposide 		
< 50,000–25,000/μL) with	• If platelet count recovers to $> 100 000/mm^3$):		

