Grade ≥ 2 bleeding	 Resume venetoclax at one dose level reduction (see Table 6). Administer carboplatin and etoposide at 50% of previous dose (see Table 7). Dose of carboplatin and etoposide can be re-escalated (even to full dose) in subsequent cycles with the 		
	approval of Medical Monitor (see Section 5.1.5.2).		
	 Administer atezolizumab at previous dose level. 		
	 If patient develops recurrent Grade 3 thrombocytopenia with Grade ≥ 2 bleeding following venetoclax dose reduction to 100 mg and two dose reductions for carboplatin etoposide, discontinue venetoclax and carboplatin etoposide during the induction phase. 		
Thrombocytopenia, Grade 4	Withhold venetoclax.		
(platelets < 25,000/µL) ^a	Withhold atezolizumab plus carboplatin and etoposide.		
	 Administer platelet transfusion if platelet count is <10,000/µL or as per institutional guidelines. 		
	 If platelet count rises to ≥ 100,000/mm³: 		
	 Resume venetoclax at one dose level reduction (see Table 6). Administer carboplatin and etoposide at 75% of previous dose (see Table 7). Dose of carboplatin and etoposide can be re-escalated (even to full dose) in subsequent cycles with the approval of Medical Monitor (see Section 5.1.5.2). 		
	 Administer atezolizumab at previous dose level. 		
	 If patient develops recurrent Grade 4 thrombocytopenia following venetoclax dose reduction to 100 mg and two dose reductions for carboplatin etoposide, discontinue venetoclax and carboplatin etoposide during the induction phase. 		
Diarrhea, Grade 3	Withhold venetoclax.		
	Withhold atezolizumab plus carboplatin and etoposide.		
	Administer anti-diarrheals per institutional guidelines (e.g.		
	loperamide 4 mg initial dose up to a maximum of 16 mg per day)		
	• Upon resolution of Grade 3 diarrhea to Grade ≤ 1:		
	 Resume treatment with venetoclax at the previous dose. Administer carboplatin and etoposide at previous dose (see Table 8). Administer ategolizumab at previous dose level 		

Event	Management
Diarrhea, Grade 3 (cont.)	 For uncontrolled Grade 3 diarrhea that occurs on adequate anti- diarrhea medication or any grade of diarrhea requiring hospitalization: Reduce venetoclax by one dose level (see Table 7). Administer carboplatin and etoposide at 75% of previous dose (see Table 8). Dose of carboplatin and etoposide can be re-escalated (even to full dose) with the approval of Medical Monitor (see Section 5.1.5.2). Administer atezolizumab at previous dose.

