Diarrhea, Grade 4	 Withhold venetoclax. Withhold atezolizumab plus carboplatin etoposide. Administer anti-diarrheals per institutional guidelines (e.g., loperamide 4 mg initial dose up to a maximum of 16 mg per day) Upon resolution of Grade 4 diarrhea to Grade ≤ 1: Resume treatment with venetoclax at one dose level reduction (see Table 7) Administer carboplatin and etoposide at 75% of previous dose (see Table 8). Dose of carboplatin and etoposide can be re-escalated (even to full dose) with the approval of Medical Monitor (see Section 5.1.5.2). Administer atezolizumab at previous dose. For uncontrolled Grade 4 diarrhea that occurs despite adequate anti-diarrhea medication or any grade of diarrhea requiring hospitalization: Further reduce venetoclax by one dose level (see Table 7). Administer carboplatin and etoposide at 75% of previous dose (see Table 8).
Hepatic event, Grade 2	 Monitor LFTs more frequently until return to baseline Events of > 5 days duration: Withhold atezolizumab for up to 12 weeks after event onset. Initiate treatment with corticosteroids equivalent to 1–2 mg/kg/day oral prednisone. If event resolves to Grade 1 or better, resume atezolizumab. If event does not resolve to Grade 1 or better while withholding atezolizumab, permanently discontinue atezolizumab and contact Medical Monitor.

Table 10Management Guidelines for Specific Adverse Events with
Venetoclax, Atezolizumab, and Carboplatin Etoposide (cont.)

Table 10 Management Guidelines for Specific Adverse Events with Venetoclax, Atezolizumab, and Carboplatin Etoposide (cont.)

Event	Management	
Hepatic event, Grade 3	 Discontinue atezolizumab. Withhold venetoclax. Withhold carboplatin and etoposide. If hepatic event resolves to ≤ Grade 1: Resume venetoclax at one dose level reduction (see Table 6). Administer carboplatin and etoposide at 75% of previous dose (see Table 8). 	
Hepatic event, Grade 4	Discontinue atezolizumab.Discontinue venetoclax.Discontinue carboplatin and etoposide.	

ANC = absolute neutrophil count; G-CSF = growth-colony stimulating factor.

^a Dose modifications (as specified in the table above) should be made based on ANC and platelet count assessment on Day 1 of each cycle. No dose modifications are required based on ANC and platelet count assessment done on Cycle 1, Day 8 and Cycle 1, Day 15.

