5.3.5.3 Adverse Events That Are Secondary to Other Events

In general, adverse events that are secondary to other events (e.g., cascade events or clinical sequelae) should be identified by their primary cause, with the exception of severe or serious secondary events. A medically significant secondary adverse event that is separated in time from the initiating event should be recorded as an independent event on the Adverse Event eCRF. For example:

- If vomiting results in mild dehydration with no additional treatment in a healthy adult, only vomiting should be reported on the eCRF.
- If vomiting results in severe dehydration, both events should be reported separately on the eCRF.
- If a severe gastrointestinal hemorrhage leads to renal failure, both events should be reported separately on the eCRF.
- If dizziness leads to a fall and consequent fracture, all three events should be reported separately on the eCRF.
- If neutropenia is accompanied by an infection, both events should be reported separately on the eCRF.

All adverse events should be recorded separately on the Adverse Event eCRF if it is unclear as to whether the events are associated.

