Event	Management
Non-hematologic Toxicity (Not specifically described in Table 9)	
Grade 3 or 4 non-hematologic events	 Delay venetoclax for a maximum of 28 days. First episode: If improvement to Grade ≤ 1 or baseline, resume previous doses of venetoclax. For subsequent episodes: If improvement to Grade ≤ 1 or baseline, restart venetoclax at one dose level reduction. Certain treatment-emergent non-hematologic adverse events (e.g., venous thromboembolic events) may be managed and become clinically stable following medical intervention but may not improve to Grade ≤ 1 according to the NCI CTCAE definitions. In such cases, if a patient is clinically stable, resumption of study drug may be possible after consultation with the Medical Monitor.
Grade 2 related non- hematologic toxicity	 Delay treatment with venetoclax until resolution to Grade ≤ 1 (or baseline status) for a maximum of 28 days. After resolution, resume full dose of venetoclax
Grade 1 non-hematologic toxicity	No dose reduction or delay.

Toxicities associated or possibly associated with atezolizumab treatment should be managed according to standard medical practice. Additional tests, such as autoimmune serology or biopsies, should be used to evaluate for a possible immunogenic etiology.

Although most immune-mediated adverse events observed with immunomodulatory agents have been mild and self-limiting, such events should be recognized early and treated promptly to avoid potential major complications. Discontinuation of atezolizumab may not have an immediate therapeutic effect, and in severe cases, immune-mediated toxicities may require acute management with topical corticosteroids, systemic corticosteroids, or other immunosuppressive agents.

The investigator should consider the benefit–risk balance a given patient may be experiencing prior to further administration of atezolizumab. In patients who have met the criteria for permanent discontinuation, resumption of atezolizumab may be considered if the patient is deriving benefit and has fully recovered from the immune-mediated event. Patients can be re-challenged with atezolizumab only after approval has been documented by both the investigator (or an appropriate delegate) and the Medical Monitor.

PULMONARY EVENTS

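### The highest-grade rule for concurrent toxicities in Section 5.1.5 can select a less restrictive dose than a lower-grade row requires for the same drug, and the protocol states no order of precedence

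*Combined protocol and SAP*

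**What the plan says.** The first bullet of Section 5.1.5 reads: "When several toxicities with different grades of severity occur at the same time, the dose modifications should be according to the highest grade observed". The rows it has to choose between include:

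- **Venetoclax, Grade 3–4 febrile neutropenia** (Table 10, Section 5.1.6.3): "Resume venetoclax at one dose level reduction (see Table 6").
- **Venetoclax, Grade 3 or 4 non-hematologic event without a row of its own** (Appendix 12): "First episode: If improvement to Grade ≤ 1 or baseline, resume previous doses of venetoclax".
- **Chemotherapy, Grade 3 thrombocytopenia with Grade ≥ 2 bleeding** (Table 10): "Administer carboplatin and etoposide at 50% of previous dose (see Table 7").
- **Chemotherapy, Grade 4 diarrhea** (Tables 8 and 10): 75% of the previous dose.
- **Chemotherapy, neurotoxicity** (Section 5.1.5.3, below Table 8): "For Grade 3 or 4 neurotoxicity, chemotherapy should be resumed at 50% of the previous dose upon improvement or discontinued immediately".

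Other text bears on the choice. Section 3.3.2.3 says venetoclax should be reduced under Table 6 for high-grade neutropenia, febrile neutropenia, thrombocytopenia and diarrhea, and makes dose modifications subject to Medical Monitor approval. Section 5.1.5.3 gives the lower dose when neutrophils and platelets both call for an adjustment. The rest of Section 5.1.5 spares the other components when a toxicity is due solely to one, and gives the investigator discretion.

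**The concern.** Choosing by grade is safe only if, for each drug, a higher-grade row is never more lenient than a lower-grade row for another toxicity. The tables do not have that property. A site that applies the bullet as written can give more drug to a patient with two severe toxicities than one of those toxicities alone would allow.

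The venetoclax combination is clinically plausible. Section 5.1.4.3 states: "Serious infection is an important identified risk for venetoclax". Section 5.3.5.3 keeps the two events apart: "If neutropenia is accompanied by an infection, both events should be reported separately on the eCRF". The chemotherapy combination pairs thrombocytopenia with diarrhea, and Section 5.1.6.3 lists both among the main overlapping toxicities expected. At stake are patient safety and consistent dosing across the roughly 10–12 sites (Section 9.5).

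**Working it through.** The plan gives no figure to reproduce. The check sets the rows side by side, applies the bullet, and compares the result with the strictest row for the same drug.

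| Concurrent events | Drug | Lower-grade row | Higher-grade row | Bullet selects |
|---|---|---|---|---|
| Grade 3 febrile neutropenia + first Grade 4 infection | Venetoclax | One level down (Table 10) | Previous dose (Appendix 12) | Previous dose |
| Grade 3 thrombocytopenia with Grade ≥ 2 bleeding + Grade 4 diarrhea | Chemotherapy | 50% (Table 10) | 75% (Tables 8 and 10) | 75% |
| Grade 3 neurotoxicity + Grade 4 diarrhea | Chemotherapy | 50% or stop (Table 8 and text below) | 75% (Tables 8 and 10) | 75% |

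Infection falls to Appendix 12 because no other table has a row for it. Appendix 12 is limited to events not described in Table 9, which is etoposide dosing in renal impairment; Table 10 is probably meant. Infection appears in neither.

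Only the named drug is affected in each case. In the first, chemotherapy is 75% under either row (Table 7 for fever with low neutrophils, Table 8 for other Grade 3 or 4 events). In the second, both rows lower venetoclax one level. In the third, the diarrhea row already lowers venetoclax one level.

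**Size, venetoclax.** Previous dose divided by the next level down in Table 6:

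- 800/600 = 1.33
- 600/400 = 1.5
- 400/200 = 2.0
- 200/100 = 2.0

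Below 100 mg the next step is to stop.

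**Size, chemotherapy, starting from full dose.**

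- Etoposide: 3 × 100 = 300 mg/m² per cycle; 75% = 225 and 50% = 150; difference 75 mg/m².
- Carboplatin: AUC 5 × 0.75 = 3.75 and 5 × 0.50 = 2.5. At the 750 mg maximum (Section 4.3.2.4), 562.5 mg against 375 mg; difference 187.5 mg.
- Ratio: 0.75/0.50 = 1.5.

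**Platelet rows.** This inconsistency does not depend on the bullet. Table 7 gives 75% for platelets below 25,000/µL, and 50% for platelets below 50,000/µL with Grade ≥ 2 bleeding. A patient at 20,000/µL with Grade 2 bleeding meets both. In Table 10 the Grade 4 thrombocytopenia row gives 75% with no bleeding qualifier, while the Grade 3 row with bleeding gives 50%. Read literally, the bleeding patient with the lower count gets 1.5 times the chemotherapy. The lower-dose sentence in Section 5.1.5.3 concerns neutrophils together with platelets, not two platelet rows.

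**The case against.** The strongest reply is that the protocol already states the stricter action. Section 3.3.2.3 calls for venetoclax reduction after high-grade febrile neutropenia, and the text below Table 8 is unconditional on Grade 3 or 4 neurotoxicity. Appendix 12 is a residual row, and nothing in it says the febrile neutropenia row lapses. Medical Monitor approval (Section 3.3.2.3), medical judgment on the type and severity of toxicity (Section 5.1.5.1) and investigator discretion (Section 5.1.5) all stand between the bullet and the patient.

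Much of this stands. A reader might infer that the protocol as a whole directs sites to the higher dose, or is silent on the right action. The documents do not support that: the intended venetoclax and neurotoxicity actions can be read from other sections. What is missing is precedence. Those sections contradict the bullet, and none says which prevails. The safeguards allow a departure from the default but do not correct it, and attribution to the causal drug does not choose between two rows for one drug.

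Three further limits hold:

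- **Neurotoxicity is the weaker example.** It is not among the risks named for etoposide, carboplatin or venetoclax (Sections 5.1.2–5.1.4) or the overlapping toxicities. The named neurologic risks belong to atezolizumab (Section 5.1.1). If the event is attributed solely to that drug, Section 5.1.5 leaves chemotherapy unmodified.
- **The venetoclax example is specific.** The febrile neutropenia must be Grade 3 and the infection Grade 4. If both are Grade 4 the bullet does not apply, though no other rule then settles the choice.
- **Atezolizumab is not part of the point.** Section 4.3.2.1 allows no dose modification, and Appendix 13 requires documented investigator and Medical Monitor approval before rechallenge once discontinuation criteria are met.

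**Conclusion.** The concern holds in this form: a stated default can yield a less restrictive dose than another applicable row for the same drug, and it conflicts with text showing that the stricter dose is intended. When that happens, venetoclax is 1.33 to 2.0 times, and chemotherapy 1.5 times, the stricter dose. The Table 7 and Table 10 platelet rows are a separate inconsistency of the same 1.5-fold size.

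The conclusion assumes a literal reading of the bullet, an infection handled under Appendix 12 as a first episode, and toxicities not attributed solely to another component. The dose ratios compare table entries. They do not measure clinical impact, and neither would a count of conflicting row pairs, because the documents give no rate at which these events occur together. A reader might also infer an effect on the trial's efficacy or sample-size results; no endpoint definition or statistical figure depends on this rule. It is a patient-safety and dosing-consistency point that should be corrected.

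**What to change.** Replace the first bullet of Section 5.1.5 with:

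> When several toxicities occur at the same time, apply for each study drug the most restrictive action required by any toxicity not attributed solely to another component; a discontinuation criterion met by any such event applies regardless of the grade of the others.

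In Table 7, add *without Grade ≥ 2 bleeding* to the row for platelets below 25,000/µL. In the Grade 4 thrombocytopenia row of Table 10, state 75% of the previous dose, or 50% with Grade ≥ 2 bleeding. The Grade 4 neutropenia row needs no change: the lower-dose sentence in Section 5.1.5.3 covers neutrophils with platelets, and Table 7's low-platelet rows already apply whatever the neutrophil count.

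With these changes the first case lowers venetoclax one level, the second gives chemotherapy at 50%, and the third gives 50% or stops it.

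The cost is one sentence and two table rows, with no added visits, data or patients. The change extends the lower-dose principle of Section 5.1.5.3, adds no reduction that a table does not already call for, and leaves the chemotherapy re-escalation provisions as they are.

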5.1.5.1 Venetoclax Dose Modifications

Although patients with adverse events are to be managed according to the particular clinical circumstances based on the investigator's medical judgment, dose reduction of venetoclax by one and, if needed, two dose levels will be allowed depending on the type and severity of the toxicity encountered (see Table 6). Each dose reduction of venetoclax will occur by 200 mg (e.g., the starting dose of 800 mg will be reduced to 600 mg, then to 400 mg). Dose reduction by two dose levels (e.g., reducing from 800 mg to 400 mg directly) is not permitted. Such patients may continue to receive atezolizumab plus carboplatin and etoposide at the discretion of the investigator in the induction phase and atezolizumab as a single agent in the maintenance phase. Patients requiring clarification regarding management of adverse events and dosing and all patients requiring more than two dose reductions should be discussed with the Medical Monitor. All dose modifications/adjustments must be clearly documented in the patient's source notes and eCRF.

Once a dose has been reduced for a given patient, all subsequent cycles should be administered at the reduced dose level, unless further dose reduction is allowed. Dose re-escalation is not allowed.

Venetoclax Current Dose Level	Venetoclax Dose Reduction
800 mg	600 mg
600 mg	400 mg
400 mg	200 mg
200 mg	100 mg
100 mg	Discontinue venetoclax

Table 6 Venetoclax Dose Reduction

5.1.5.2 Atezolizumab Dose Modification, Treatment Delays, or Treatment Discontinuation and Management of Specific Adverse Events

There will be no dose reduction for atezolizumab in this study. Patients may temporarily suspend study treatment with atezolizumab for up to 105 days beyond the last dose if they experience an adverse event that requires a dose to be withheld. If atezolizumab is withheld because of adverse events for more than 105 days beyond the last dose, then the patient will be discontinued from atezolizumab/ treatment. Exceptions require Medical Monitor approval.

If a patient must be tapered off steroids used to treat adverse events, atezolizumab may be withheld for additional time beyond 105 days from the last dose until steroids are discontinued or reduced to prednisone dose (or dose equivalent) \leq 10 mg/day. The acceptable length of interruption will depend on agreement between the investigator and the Medical Monitor.

Dose interruptions for reason(s) other than adverse events, such as surgical procedures, may be allowed with Medical Monitor approval. The acceptable length of interruption will depend on agreement between the investigator and the Medical Monitor.

5.1.5.3 Chemotherapy Dose Modifications, Treatment Delays, or Treatment Discontinuation and Management of Specific Adverse Events

Dose modifications for carboplatin and etoposide are permitted for toxicity according to the prescribing information and local standard of care.

Dose modification guidelines are provided below.

Treatment with carboplatin or etoposide should be discontinued if a patient experiences any hematologic or non-hematologic Grade 3 or Grade 4 toxicity after two dose reductions or treatment is delayed for more than 63 days due to toxicities.

Hematologic Toxicity

At the start of each cycle, the ANC should be $\geq 1500/\mu$ L and the platelet count should be $\geq 100,000/\mu$ L. Treatment should be delayed for up to 63 days to allow sufficient time for recovery. Growth factors may be used in accordance with American Society of Clinical Oncology (ASCO) and NCCN guidelines (Smith et al. 2006; NCCN 2019) or as per institutional guidelines. Upon recovery, dose adjustments at the start of a subsequent cycle will be made on the basis of the lowest platelet and neutrophil values from the previous cycle (see Table 7). Increased frequency of lab assessments (e.g., neutrophil and platelet counts) on Cycle 1, Day 8 and Cycle 1, Day 15 are used to better characterize the impact of and response to treatment. Since such assessments are not routinely performed, they will not be used for dose modifications for subsequent cycles. Therefore, Cycle 2 dose adjustments will be based on assessments performed after Cycle1, Day 21.

In the event that dose adjustments are needed for both ANC and platelets, patients are to receive the lower dose.

Table 7 Chemotherapy Dose Modification for Hematologic Toxicities

Toxicity ^a	Dose	
ANC <500/µL and platelets ≥50,000/µL	75% of previous dose	
Platelets <25,000/μL, regardless of ANC	75% of previous dose	
Platelets $<$ 50,000/µL with Grade \ge 2 bleeding, regardless of ANC	50% of previous dose	
ANC < 1000/ μ L plus fever of \geq 38.5°C	75% of previous dose	

^a Nadir of prior cycle with the exception of Cycle 1, where neutrophil and platelet assessments performed after Cycle 1, Day 21 will be used for dose adjustment.

The dose of chemotherapy can be re-escalated (even to full dose) in subsequent cycles if cytopenias have improved due to venetoclax reduction with the approval of Medical Monitor. This is to try to maintain dose intensity of standard of care chemotherapy, especially if cytopenias resolve with venetoclax dose reductions.

Investigators should be vigilant and alert to early and overt signs of myelosuppression, infection, or febrile neutropenia so that these complications can be promptly and appropriately managed. Patients should be made aware of these signs and encouraged to seek medical attention at the earliest opportunity.

If chemotherapy is withheld because of hematologic toxicity, full blood counts (including differential WBC) should be obtained weekly until the counts reach the lower limits for treatment as outlined. The treatment can then be resumed.

No dose reductions are recommended for anemia. Patients should be supported per the investigator's institution's guidelines.

Non-Hematologic Toxicity

For a non-hematologic toxicity (see Table 8), treatment should be delayed for up to 63 days until resolution to less than or equal to the patient's baseline value (or Grade \leq 1 if the patient did not have that toxicity at baseline). Dose reductions at the start of the subsequent cycle should be made on the basis of non-hematologic toxicities from the dose administered in the preceding cycle. Table 8 provides recommended dose modifications for non-hematologic toxicities.

Table 8 Dose Modifications or Treatment Discontinuation for Non-Hematologic Toxicities

Toxicity		Adjusted Dose as % of Previous Dose ^a
Diarrhea	Grade 3 or 4 $^{\rm b}$	75%
Nausea/vomiting	Grade 3 or 4 °	75%
Neurotoxicity	Grade 2	75%
	Grade 3 or 4	50% or permanent discontinuation
Transaminase elevation	Grade 3	75%
	Grade 4	Discontinue
Other	Grade 3 or 4	75%

AUC=area under the concentration-time curve.

^a If deemed appropriate by the investigator, adjust carboplatin dose to the specified percentage of the previous AUC.

^b Grade 3 or 4 diarrhea that occurs on adequate anti-diarrhea medication or any grade of diarrhea requiring hospitalization.

^c Despite the use of anti-emetics.

Diarrhea should be controlled with adequate anti-diarrheal medication. Nausea and/or vomiting may be controlled with adequate anti-emetics. For Grade 3 or 4 neurotoxicity, chemotherapy should be resumed at 50% of the previous dose upon improvement or discontinued immediately (based on investigator's clinical judgment).

Suggested recommendations for dose modification of etoposide for renal impairment are provided in Table 9.

Table 9 Etoposide Dose Modification for Renal Impairment

Creatinine Clearance (mL/min)	Etoposide Dose	
> 50	100%	
15–50	75% of dose	

